8. DATA AND SAFETY MONITORING

The specific monitoring plan for this study is commensurate with the risks and the size and complexity of the investigations planned. The potential risks are attributable to the use of nitrous oxide. Based on these considerations the monitoring plan involves a DSMC including [name], an attending anesthesiologist knowledgeable in nitrous oxide pharmacology, [name], an attending otolaryngologist with experience with tinnitus patients, and [name], a biostatistician with experience in conducting clinical trials. All reports of Serious Adverse Events or Unexpected Adverse Events will be investigated by the DSMC and reported to the WU HRPO/IRB per reporting guidelines.

Furthermore, the study principal investigator and study coordinator will monitor for breaches of confidentiality and other adverse events on an ongoing basis. Once the PI or study coordinator becomes aware of a reportable adverse event, the event will be reported to HRPO according to institutional guidelines.

9. DATA ANALYSIS

Standard descriptive statistics will describe the study population, responses to assessments, and severity of tinnitus. Data will be analyzed using SAS version 9.4 statistical software (SAS Institute, Inc. Cary, NC).

Aim 1. To evaluate the effect of nitrous oxide as treatment of tinnitus.

The primary efficacy parameter will be the in the change in TFI. Secondary outcome measure will be the change in MAT. **Baseline** TFI and MAT will be defined as those determined immediately before a session. **Post-treatment** TFI and MAT will be compared to **baseline** TFI and MAT at each time point. A mixed model analysis using SAS Proc Mixed procedure will be used to explore the change in TFI score after treatment as compared to after placebo through exploration of the interaction effect of time*treatment. The mixed procedure allows for exploring information from measures nested within subjects nested within treatment groups. In addition, this analytical approach allows for investigation of the carry-over effect due to cross-over design.

And finally, the number of subjects with 13 or more points difference in TFI (clinically important difference)[16] after each treatment arm will be identified and compared between active and placebo treatments using McNemars test.

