Inclusion and Exclusion Criteria	
Inclusion Criteria
 
 a) Adult men and women 18-65 years of age b) Subjective, unilateral or bilateral, non-pulsatile tinnitus for at least 6 months duration c) Either “Bothered more than a little but not a lot”, “Bothered a lot”, or “Extremely bothered” on the Global Bothersome scale d) Able to give informed consent e) Must be able to read, write, and understand English 
Exclusion Criteria
 
History of:
 
 a) Bipolar disorder b) Schizophrenia c) Schizoaffective disorder d) Substance abuse or dependence (except for remote substance abuse or dependence with remission at least 1 year prior to the study and except for nicotine use disorders) e) Acute medical illness that may pose subject at risk during nitrous oxide administration f) Active psychotic symptoms g) Patients with significant pulmonary disease and/or requiring supplemental oxygen h) Contraindication against the use of nitrous oxide: 
 a. Pneumothorax b. Bowel obstruction c. Middle ear occlusion d. Elevated intracranial pressure e. Chronic cobalamin and/or folate deficiency treated with folic acid or vitamin B12 f. Pregnant patients g. Breastfeeding women i) Previous administration of NMDA-receptor antagonists (e.g., ketamine) within the last 3 months j) Tinnitus related to cochlear implantation, retrocochlear lesion, Meniere’s Disease, or other known anatomic lesions of the ear or temporal bone k) Tinnitus related to a Workman’s Compensation claim or litigation-related event that is still pending. l) Any medical condition, which, in the opinion of the PI, confounds study results or places the subject at greater risk
Primary Outcome and Measurements	The difference in the difference in patient-reported tinnitus symptoms according to Tinnitus Functional Index (TFI) between baseline and 1 week after each intervention. Secondary outcome measure will be the same calculation performed for the Momentary Assessment of Tinnitus (MAT) questionnaire.

ABSTRACT

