Tinnitus, the perception of sound in the absence of external acoustic stimulation, is a common yet poorly understood disease that currently lacks effective front-line treatment. Many therapies focus on mitigating the effects of tinnitus on patients' quality of life, such as through habituation or masking with white noise. However, the tinnitus research literature suggests that NMDA receptor antagonists may prove to be useful in reducing tinnitus itself.[6, 9, 11, 12] Nitrous oxide belongs to the class of NMDA receptor antagonists, and additionally is widely-used, non-invasive, and has a proven safety profile. As such, nitrous oxide may be the drug of choice for testing the efficacy of NMDA receptor antagonists on reducing subjective, bothersome tinnitus.

We propose conducting a pilot randomized placebo-controlled, double-blind crossover study in which patients attend two sessions where they receive either 50% nitrous oxide in oxygen or 50% nitrogen, 50% oxygen for a period of 40 minutes. Tinnitus will be assessed using the Tinnitus Functional Index (TFI) upon enrollment, then reassessed 1 week following each intervention session. Secondly, the Momentary Assessment of Tinnitus (MAT) questionnaire will be administered at baseline before intervention, 1 hour after intervention, 1 day after intervention, and 1 week after intervention.

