5. SCREENING AND ENROLLMENT

Participants will be recruited from Washington University School of Medicine Department of Otolaryngology-Head and Neck Surgery clinics, including the Division of Audiology. The Washington University Volunteers for Health Research Participant Registry and Otolaryngology Research Participant Registry will be queried to identify potential participants. Potential participants will be screened according to inclusion and exclusion criteria over the telephone, and those who meet inclusion criteria will be invited to the 8th floor McMillan Building Clinical Research Outcomes Office to discuss study participation. The potential participant will have the opportunity to review the consent form and have questions about the study answered by the study team. The PI, or designee, will obtain written consent prior to the start of study related procedures.

We will enroll a total of 40 participants with bothersome tinnitus to achieve at least 30 evaluable participants. Participants will be offered \$50 in remuneration for their time and effort in this study, to be given upon completion of study participation.

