7. DATA COLLECTION

Assessment of Treatment Efficacy

Baseline and Treatment Efficacy Assessment Forms:

1. Demographics
2. Tinnitus Description and History Form
3. Global Bothersome Scale (GBS)
4. Tinnitus Functional Index (TFI)
5. Momentary Assessment of Tinnitus Questionnaire (MAT)
6. Patient Health Questionnaire (PHQ-9)
7. Patients' Global Impression of Change (PGIC)

The effects of the treatment will be assessed using repeat administration of GBS, TFI, MAT, PHQ-9, and PGIC.

Participants will be asked to complete forms 1-6 (detailed above) immediately before each of two sessions as **baseline assessment**, with Demographics and Tinnitus Description and History Form only required before the first session. One hour and then one day following each intervention, participants will complete EMA. One week following each session, participants will complete GBS, TFI, MAT, PHQ-9, and PGIC. These constitute the **treatment efficacy assessment**. In total, each participant will complete the baseline assessment at two timepoints and treatment efficacy assessment at 6 timepoints. The two sessions will be 14 days (2 weeks)

apart. These questionnaires can be completed online via a link provided through REDCap in an email to the participant. At 14 days after administration of nitrous oxide, we expect the effects of nitrous oxide to wear off fully and patients' tinnitus should have returned to baseline. The baseline assessment for the second session will take place no sooner than 14 days after the first session, and therefore will assess whether this washout period of 14 days is accurate. The patient will not be allowed to participate in the second arm of the study until their Global Bother Scale score is within one category of their baseline score.

Assessment of Treatment Safety

Treatment safety will be assessed at several levels: adverse events (AE) related to (i) cardiovascular status; (ii) respiratory function; (iii) central nervous system; (iv) psychiatric symptoms,.

- (i) Cardiovascular AEs, such as hyper- and hypotension, tachy-/bradycardia, will be identified by continuous hemodynamic monitoring during and after the treatment
- (ii) Respiratory AEs, such as respiratory depression and desaturation, will be identified by continuous pulse oximetry during and after treatment
- (iii) Central nervous system AEs will be assessed clinically.
- (iv) Psychiatric AEs, will be assessed clinically.

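### Is the starting score for the 13-point TFI responder count left unsettled by the abstract and the analysis section?

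*Combined protocol and SAP*

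**What the plan says.** Four places in the combined protocol and SAP bear on this point.

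- **Section 9 (Data Analysis), last paragraph.** The plan will identify "the number of subjects with 13 or more points difference in TFI (clinically important difference" after each treatment, "compared between active and placebo treatments using McNemars test". Neither a reference score nor a direction appears in that sentence.
- **Section 9, preceding paragraph, same aim.** Baseline "TFI and MAT will be defined as those determined immediately before a session", and post-treatment scores are compared with that baseline.
- **Section 7 (Data Collection).** "Participants will be asked to complete forms 1-6 (detailed above) immediately before each of two sessions as" the baseline assessment. The TFI is form 4 on that list. Only the demographics and tinnitus history forms are excused from the second session. The section adds that "each participant will complete the baseline assessment at two timepoints", and it uses the second one to check the 14-day washout.
- **Abstract.** "Tinnitus will be assessed using the Tinnitus Functional Index (TFI) upon enrollment, then reassessed 1 week following each intervention session". No TFI before session 2 is listed.

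The synopsis measures the primary outcome "between baseline and 1 week after each intervention" without saying which baseline is meant.

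**The concern.** Read alone, the responder sentence is incomplete, and the abstract seems to supply a different starting score from Sections 7 and 9. The abstract's next sentence places the secondary questionnaire (MAT) at a baseline before the intervention but places the TFI at enrollment, so the difference could look deliberate.

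If the abstract governed, two things would follow. There would be no TFI before session 2, so the session-2 change that Section 9 defines could not be computed. With one enrollment score B shared by both periods, the primary contrast would also collapse: (active week-1 score − B) − (placebo week-1 score − B) = active week-1 score − placebo week-1 score. For the responder count, the starting score decides who is a session-2 responder, and so which pairs are discordant in McNemar's test.

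The missing direction raises a separate worry. Taken literally, a worsening of 13 points would count as an event.

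**Working it through.** **1. How many TFI scores does each place imply?**

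Section 7 gives its own tally: two baseline assessments and six efficacy assessments. The six reproduce as 2 sessions × 3 follow-ups (one hour, one day, one week). The TFI is in both baseline sets and in both one-week sets, so there are 2 + 2 = 4 TFI scores per person. The abstract's list gives 1 + 2 = 3. The score in dispute is the one before session 2.

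**2. Which place governs?**

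| Place | Role | TFI before session 2? | Mentions the 13-point count? |
|---|---|---|---|
| Abstract | Summary | Not listed | No |
| Section 7 | Data-collection schedule | Yes, with a stated purpose | No |
| Section 9 | Analysis definition | Yes, it is the session baseline | Yes |

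The section that holds the count holds one definition of baseline and no competing one. Section 7 collects the score which that definition needs. The documents therefore give one analysis definition, plus a summary that leaves out a visit.

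**3. What would the other starting score do?**

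The documents give no SD, effect size, alpha or figure for this count, so everything here is assumed: 30 completers (the evaluable target in Section 5), 15 per order, equal and independent within-person errors, no carry-over, and a mean change of −13 on nitrous oxide and 0 on placebo. The event is a fall of at least 13 points.

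The two candidate session-2 changes share the week-1 score, so their correlation is 0.5. With p the probability of an event under either start,

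P(classified differently) = 2 × (p − P(event under both)).

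On nitrous oxide p = 0.5 and P(both) = 1/3, so P = 2 × (0.5 − 0.333) = 0.333 at any SD. On placebo p = Φ(−13/SD). The expected number reclassified is 15 × 0.333 + 15 × P(placebo). At SD 15 this is 5.0 + 15 × 0.220 = 8.3.

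Power is for a two-sided exact McNemar test at 0.05, from 20,000 simulated trials per case. Each pair shows the pre-session start, then the enrollment start.

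| SD of change | p, placebo | P(different), placebo | Reclassified of 30 | Power, no carry-over | Power, half the effect persisting |
|---|---|---|---|---|---|
| 8 | 0.052 | 0.078 | 6.2 | 0.97 / 0.99 | 0.98 / 0.92 |
| 12 | 0.139 | 0.175 | 7.6 | 0.80 / 0.91 | 0.79 / 0.67 |
| 15 | 0.193 | 0.220 | 8.3 | 0.61 / 0.76 | 0.61 / 0.48 |
| 20 | 0.258 | 0.264 | 9.0 | 0.38 / 0.50 | 0.38 / 0.28 |

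Without carry-over, both changes have the same distribution, so the expected responder shares are identical under either start: 50% on nitrous oxide and 5%, 14%, 19% and 26% on placebo. The reclassified participants move in both directions equally.

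If scores also drift down 5 points at each later step, the shares at SD 15 move from 63% and 30% (pre-session) to 69% and 36% (enrollment). The gap between treatments is 33 percentage points either way.

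If half the effect persists into the second period, the enrollment start counts that residue as improvement on placebo, while the pre-session start subtracts it. The power order then reverses.

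**4. What would the literal reading of direction do?**

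With no mean change, counting both directions doubles the share of events. At SD 15 it goes from 19.3% to 2 × 19.3% = 38.6%. Under the step 3 assumptions, power at SD 15 with the pre-session start falls from 0.61 to about 0.15. That would be a real loss, but only for a count that adds people who worsened to people who improved.

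**The case for a change.** The strongest case for acting has three parts.

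- A coordinator who worked from the abstract would skip the session-2 TFI. That score cannot be recovered later, and its loss would reach the primary analysis and the washout check as well as the count.
- The more powerful starting score depends on carry-over that nobody knows in advance, so the choice should be fixed before data are seen.
- No section states the direction, and clearer wording would cost two sentences.

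The first part requires staff to follow a summary over the section written to direct them. That section says the same thing in more than one way: forms before each session, a short list of forms excused from the second session, a count of two baselines, and a use for the second one. The second part is right in principle, but Section 9 already fixes the choice. The third part is correct as an observation. The direction is unstated, and adding it would do no harm. But the aim is efficacy, the threshold is described as clinically important, and the test compares active with placebo. A count that pooled improvement with deterioration would not address that aim, and an analyst would not build it. The primary mixed model uses signed change and is unaffected.

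**Conclusion.** The concern does not hold as a fault in the plan. Anyone who follows Sections 7 and 9 collects all four TFI scores, computes each session's change from that session's own baseline, and obtains a valid paired count and a valid primary analysis. The abstract's omission is clerical. The missing direction is a gap that analysts fill sensibly.

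The figures do not alter this. The 6 to 9 reclassified participants and the power differences rest on assumed SDs, means and error structure, and they measure a departure from the stated definition. They show no consistent harm either: at SD 15 the stated pre-session start has lower power without carry-over (0.61 against 0.76) and higher power with it (0.61 against 0.48). The count is also a supporting analysis in a pilot, listed after the mixed model. An editor could align the abstract and add a word for direction at the next revision, but no planned result depends on it.

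The conclusion assumes that the data-collection and analysis sections govern over the abstract, and that the count means improvement.

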6. METHODS

Study Design

This is a prospective, randomized, double-blinded, placebo-controlled crossover trial where 40 patients will undergo two treatment sessions in randomized order. In one session, subjects will receive up to 50% nitrous oxide/50% oxygen for 40 minutes ("Treatment"). In the other session, subjects will receive up to 50% nitrogen [inert]/50% oxygen for 40 minutes ("Placebo"). The two sessions will be held 2 weeks apart and will be indistinguishable from each other in setting, setup, and monitoring.

No pre-enrollment laboratory assessments will be required. However, a health history will be taken at screening.

Randomization

Each participant will be randomly assigned to either the “Treatment first” or “Placebo first” group. The randomization scheme will use permuted blocks of randomly varying sizes generated by the study statistician using SAS statistical software and a password-protected Microsoft Excel spreadsheet will be used to create and store the study IDs and the randomization order. Each block will contain equal numbers of assignments to the treatment first and placebo first in randomized order. To account for the anticipated 20% dropout rate (i.e., as a result of withdrawal, being lost to follow-up, and so on), the randomization table will be generated for 50 subjects.

Blinding

Participants will be blinded to the randomization order. Nitrous oxide is a colorless and odorless gas, which makes it unlikely for participants to identify the group assignment. Likewise, the study setup will be identical for both sessions, which will make an inadvertent unblinding of the study unlikely. For the anesthesiology team responsible for the administration of the nitrous oxide treatment, the group assignment will be known. This team is completely separate from the team assessing the study outcomes, which will be blinded to the treatment received. Treatment administration and outcomes assessment will also be physically separated in different rooms within the Clinical Research Unit (CRU) to prevent unblinding. To assess the integrity of the blind, subjects will be asked immediately after each administration to guess which treatment – active or placebo they just received.

Setting

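### McNemar's test on 13-point TFI responders ignores the randomised sequence: conservative with equal sequences and shifted with unequal ones if response differs between sessions (minor, supporting analysis)

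*Combined protocol and SAP*

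**What the plan says.** Section 6 (Randomization) sets up a two-sequence crossover: "Each participant will be randomly assigned to either the “Treatment first” or “Placebo first” group". Balance is planned at entry: "Each block will contain equal numbers of assignments to the treatment first and placebo first in randomized order". Balance among completers is not protected. Section 5 reads "We will enroll a total of 40 participants with bothersome tinnitus to achieve at least 30 evaluable participants", and Section 6 sizes the randomisation table "To account for the anticipated 20% dropout rate".

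Section 9 gives the responder analysis last, after the mixed model for the TFI score. It takes "the number of subjects with 13 or more points difference in TFI (clinically important difference"), which "after each treatment arm will be identified and compared between active and placebo treatments using McNemars test". Each response is measured from its own session's baseline: baseline "TFI and MAT will be defined as those determined immediately before a session". No sequence or session factor is attached to this test. The one crossover remark in Section 9 concerns carry-over in the mixed model. That is neither a session adjustment nor part of the responder test. No responder rates, session effect, significance level or power are stated.

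**The concern.** McNemar's test compares the participants who respond on nitrous oxide only with those who respond on placebo only, pooled over both sequences. Someone who responds only in the first session, whatever the gas, counts for nitrous oxide if it came first and for placebo if placebo came first. A difference between sessions therefore enters the comparison of the gases. With equal sequences it cancels in expectation and only inflates the variance that the test assumes. With unequal sequences part of it remains in the estimate.

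This is the plan's only analysis of clinically important change. It rests on about 30 participants and a small number of discordant pairs, so a shift of one pair can be seen in the result.

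**Working it through.** **The plan's own figure.** The table of 50 allows for 20% dropout on 40: 40/(1 − 0.20) = 50, reproduced. Also 40 × 0.80 = 32, consistent with at least 30 evaluable; falling to 30 is a loss of 10/40 = 25%. The checks below take 20/20 at entry and 30 completers.

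**Assumptions not in the plan.** Two-sided 0.05, uncorrected McNemar statistic, and responder rates by session as stated at each step.

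**Step 1: shift with no gas effect.** Let p1 and p2 be the response rates in sessions 1 and 2, and nA and nB the completers in the two sequences.

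Shift = (nA − nB)/(nA + nB) × (p1 − p2)

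With 30% and 10%:
- 15/15: 0
- 17/13: (4/30) × 0.20 = 2.7 points
- 18/12: (6/30) × 0.20 = 4.0 points, or 0.04 × 30 = 1.2 pairs
- 20/10: (10/30) × 0.20 = 6.7 points

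With 40% and 22%, the rates of the model in Step 4, the shift at 18/12 is 0.2 × 0.18 = 3.6 points. Simulation gave +3.5 at 18/12 and −3.6 at 12/18, and 0 for an estimate that weights the sequences equally.

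**Step 2: variance at 15/15.** With 30%/10% and independence within participant, P(session 1 only) = 0.30 × 0.90 = 0.27 and P(session 2 only) = 0.10 × 0.70 = 0.07. The expected number of discordant pairs is 30 × 0.34 = 10.2. The true variance of the net count, relative to the one McNemar uses, is 1 − (0.20)²/0.34 = 0.88. The test's standard error is therefore too large by a factor of √(1/0.88) = 1.07.

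**Step 3: McNemar's type I error, by exact enumeration, no gas effect.**

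| Response rate, session 1 / session 2 | 15/15 | 17/13 | 18/12 | 20/10 |
|---|---|---|---|---|
| 20% / 20% | 4.3% | 4.3% | 4.3% | 4.3% |
| 30% / 10% | 3.1% | 3.7% | 4.4% | 6.9% |
| 40% / 10% | 2.4% | 3.3% | 4.6% | 9.3% |
| 50% / 10% | 1.7% | 3.1% | 5.0% (4.95%) | 12.4% |

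The total hides the direction. At 18/12 with 30%/10%, the 4.4% divides into 3.85% in favour of the gas given first in the larger sequence and 0.58% in favour of the other. At 20/10 the division is 6.6% and 0.3%.

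**Step 4: power under an assumed gas effect.** The model is logistic, with between-participant SD 1, gas log-odds 1.5, and second-session log-odds −1 (order effect) or 0 (none). With the order effect, placebo response is 40% then 22%, and nitrous oxide 70% then 50%. Prescott's test is in its asymptotic permutation-variance form.

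| Order effect | Nitrous oxide first / placebo first | McNemar | Prescott |
|---|---|---|---|
| Yes | 15/15 | 0.65 | 0.69–0.70 |
| Yes | 12/18 | 0.53 | 0.68 |
| Yes | 18/12 | 0.77 | 0.68 |
| No | 15/15 | 0.70 | 0.71 |
| No | 20/10 | 0.70 | 0.66 |

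The swing in McNemar's power follows its estimate. The expected difference is 0.5 × (0.70 − 0.22) + 0.5 × (0.50 − 0.40) = 0.29 at 15/15, but 0.6 × 0.48 + 0.4 × 0.10 = 0.328 at 18/12 and 0.4 × 0.48 + 0.6 × 0.10 = 0.252 at 12/18.

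With the gas effect removed and the order effect kept, McNemar's size at 15/15 was about 0.037 (repeat simulations ranged from 0.033 to 0.037). Prescott's stayed at about 0.05.

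**Step 5: how often the sequences end up unequal.** If 10 of 40 are lost without regard to sequence, the split is hypergeometric. A gap of 4 or more occurs in 27% of trials and of 6 or more in 6.5%. Exactly 12/18 has probability C(20,12) × C(20,18)/C(40,30) = 125,970 × 190/847,660,528 = 2.8%. A 20/10 split in either direction has probability 2 × 184,756/847,660,528 = 0.04%. Averaged over all splits, power is 0.65 for McNemar and 0.69 for Prescott, and the bias is zero.

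**The case against.** **The order effect is hypothetical.** A reader might infer one from the entry requirement of bothersome tinnitus, since regression to the mean would favour session 1. The documents do not establish this. Eligibility uses the Global Bothersome scale at screening, whereas response is a TFI change from a fresh baseline before each session, so some of that regression may be over before the first baseline. Section 7 also requires bother to be back within one category of baseline before the second session. This objection stands: the sizes above are illustrations, and with no order effect the two tests perform almost alike except at very unequal splits.

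**The power loss is easily overstated.** Quoting only the 12/18 split (0.53 against 0.68) would suggest a general loss; at 18/12 McNemar has the higher figure, 0.77 against 0.68. That also stands. But the gain is the same bias pointing the other way, so it is no credit to the test.

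**McNemar's test is not generally anti-conservative.** A reader might infer an inflated false-positive rate. In the cases computed the total exceeds 5% only at 20/10, which is very rare when loss is unrelated to sequence. What remains at moderate splits is the lopsided direction of the errors.

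**Not every session-adjusted test helps.** Under a different assumed gas effect, the Mainland-Gart chi-square had power 75.5% against McNemar's 77.1% at 15/15, and its Fisher form was very conservative (size 0.3% to 2.0%). Mainland-Gart drops the concordant pairs that Prescott's test uses, so this bears on which adjusted test to choose.

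**The role is small.** This is a pilot, the primary analysis is the mixed model, and no decision rule depends on the responder test. That settles the point as minor.

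**Conclusion.** The point holds as a minor improvement to a supporting analysis. The mechanism is algebra: McNemar's test ignores the sequence by which the trial randomises, so any session difference makes it conservative when the sequences are equal and shifts its estimate when they are not. The size depends on assumed session rates. At 15/15 the cost is about 4 to 5 points of power; at 18/12 it is a shift of about 3.5 points towards the gas given first in the larger sequence.

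It would go too far to call the responder comparison systematically biased. With loss unrelated to sequence the bias averages to zero over trials, although it is present in whatever split the trial ends with. It becomes systematic only if loss depends on the first gas. The Section 7 condition for entering the second session makes that possible, but nothing in the documents shows that it will happen. The primary TFI analysis is a separate model and is not touched by this point.

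**What to change.** In Section 9, replace McNemar's test with Prescott's test. Score each participant +1 (responder in session 1 only), 0 (both or neither) or −1 (session 2 only), and compare the scores between the two randomised sequences.

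Name the version in advance. The asymptotic permutation-variance form kept its size at about 0.05. The fully exact form is conservative at about 30 participants (size 0.02 to 0.03), although against exact McNemar it still had power 0.58 against 0.55 at 15/15 and 0.59 against 0.43 at 12/18 under the order effect.

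Report the responder difference with equal weight on the two sequences, which is half the difference between their mean scores, with a confidence interval. Report completers by sequence beside it. McNemar's result can stay as a descriptive figure.

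The cost is a sentence or two in Section 9 and a few lines of SAS, with no new data or participants. The downsides are a less familiar test and a small loss of power at very unequal splits if there is no order effect (0.66 against 0.70 at 20/10).
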